I will conduct the clinical trial in accordance with Good Clinical Practice, Declaration of Helsinki, National Statement on Ethical Conduct in Human Research 2007 (as updated), Australian Code for the Responsible Conduct of Research 2018 and the moral, ethical and scientific principles that justify clinical research. The clinical trial will be conducted in accordance with all relevant laws and regulations relating to clinical studies and the protection of participants.

I agree to adhere to the protocol as approved by the Human Research Ethics Committee/s in all circumstances other than where necessary to protect the participant's wellbeing.

**Coordinating Principal
Investigator name:**

A/[name]

**Coordinating Principal
Investigator signature:**

Date of signature:

08 August 2023

4. Study Synopsis

Long title	MAIL, GP & SCALE trial: A general practice-led intervention to increase National Bowel Cancer Screening Program participation.															
Short title	MAIL, GP & SCALE trial															
Lead Investigator	A/[name]															
Aims, Objectives and Outcome	
This study aims to pilot a co-designed general practice-led intervention and implementation strategies in up to 100 general practices in New South Wales (NSW) and Western Australia (WA).
 
The objectives of the pilot trial are to:
 
 1. Increase the number of guideline-appropriate CRC screening recommendations provided. 2. Increase the number of guideline-appropriate CRC screening tests completed. 															
Study Design	The study is a hybrid type 2 effectiveness-implementation intervention trial that will be conducted in up to 100 general practices to test the effectiveness of a general practice-led intervention and a suite of implementation strategies.															
Blinding/Masking	This will be a single-blinded cluster randomised controlled clinical trial. Only the trial investigators involved in the intervention delivery will know the allocation. Participants will be allocated to either the control or intervention and monitored through the trial by the Clinical Trial Coordinators (CTC). Due to the nature of the intervention and implementation support, practices may discern their allocation.															
Study Setting and Data Collection	This study will recruit up to 100 General Practices within Primary Health Network (PHN) regions of New South Wales (NSW) and Western Australia (WA). Data collection will be facilitated by CTCs.															
Study Duration	
  
 Timeframe	Activity	
   
 November 2022 - February 2023	Complete co-design and refinement of multicomponent intervention (University of Sydney HREC 2022/755)	
 
 August 2023	Ethics approval (University of Sydney Clinical Trials)	
 
 January – August 2023	Engagement with PHNs and establishment of research agreements	
 
 August 2023	Recruitment of CTCs	
 
 September 2023	General Practice Recruitment	
 
 October 2023	Baseline data collection	
  
		Timeframe	Activity	November 2022 - February 2023	Complete co-design and refinement of multicomponent intervention (University of Sydney HREC 2022/755)	August 2023	Ethics approval (University of Sydney Clinical Trials)	January – August 2023	Engagement with PHNs and establishment of research agreements	August 2023	Recruitment of CTCs	September 2023	General Practice Recruitment	October 2023	Baseline data collection
Timeframe	Activity															
November 2022 - February 2023	Complete co-design and refinement of multicomponent intervention (University of Sydney HREC 2022/755)															
August 2023	Ethics approval (University of Sydney Clinical Trials)															
January – August 2023	Engagement with PHNs and establishment of research agreements															
August 2023	Recruitment of CTCs															
September 2023	General Practice Recruitment															
October 2023	Baseline data collection															

	March - August 2024	Delivery of intervention
	March - August 2024	Implementation support of intervention arm
	March - August 2024	Monitor of control arm (usual care)
	September - October 2024	Post-intervention data collection
	October 2024	Effectiveness evaluation
Intervention	
The intervention is a multi-component, co-designed general practice-led intervention designed based on the evidence review and co-design process in a larger project, MAIL, GP & SCALE. The co-design process was completed in April 2023 (University of Sydney HREC 2022/755). The intervention comprises the following components:
 
 1. Decision support aids 2. Electronic point-of-care prompt 3. Clinical system enhancement 4. Education 
The intervention will be provided after an initial six months of usual care and data collection. The 6-month period between recruitment and intervention delivery is being used as a wash out period to ensure best measurement of study effects. The intervention will be supported by the CTC. The CTC will guide and facilitate the implementation strategies identified in the evidence review and through the co-design process.
	
Number of participants	The trial includes up to 100 general practices within the jurisdictions of NSW and WA. There will be 50 practices per jurisdiction, with 25 practices randomly allocated to a control arm and 25 randomly allocated to an intervention arm in each jurisdiction.	
Population	The target population residing within NSW and WA is General Practices, including GPs, practice nurses and practice staff.	
Selection and enrolment	
Inclusion criteria:
 
 • Has at least two full-time equivalent GPs willing to participate in the trial • Nominated Practice Champion who is willing and able to liaise with the Daffodil Centre research team • Uses Medical Director software • Uses Pen CS, Polar or Primary Sense • Available over the trial period October 2023 – October 2024 • Windows 10 or high, i5/i7 16GB processing or willing to upgrade • Has over 1000 active patients and sees minimum of 35 adult patients per day 
Exclusion criteria:
 
 • Shares server with another practice • Uses paper-based medical records • Does not share data with PHN 	

5. List of Study Documents

The following table lists each of the study documents:

Appendix	Document Title	Purpose
Recruitment Templates		
1A	General practice recruitment templates	Will be provided to CTC and used to approach and recruit general practices into the study.
1B	General Practitioner and Practice Staff recruitment templates	Will be provided to CTC and used to approach and recruit GPs and practice staff into the study.
1C	General practice recruitment study questionnaires	Will be provided to CTC and used to approach and recruit GPs and practice staff to participate in study questionnaires.
Participant Information Statements		
2A	General practice PIS	Provide a brief overview of the study and general practice requirement.
2B	Individual GP and general practice staff PIS	Provide a brief overview of the study and requirements specific to GPs and practice staff. Obtain GP and practice staff consent to participate in the study.
Participant information and Consent Forms		
3A	General practice PCF	To obtain general practice consent to participate in the study.
3B	Individual GP and general practice staff PCF	To obtain GP and practice staff consent to participate in the study.
Data Collection Tools		
4A	Clinician and general practice staff IPSBQ questionnaire pre-trial	To be completed by all participating GPs and practice staff. Will be used to collect pre-trial information from general practice staff. This survey will assess current awareness of bowel cancer screening and use of the NCSR HCP portal and behaviour change using a modified version of the IPSBQ questionnaire.
4B	Clinician and general practice staff IPSBQ questionnaire post-trial	To be completed by all participating GPs and practice staff. Will be used to collect post-trial information from general practice staff. This survey will assess current awareness of bowel cancer screening and use of the NCSR HCP portal as well as behaviour change using a modified version of the IPSBQ questionnaire.
4C	Implementation Outcomes survey mid-trial	To be completed by all participating GPs and practice staff of the intervention arm. Will be used to collect mid-trial information from general practice staff. This survey will assess implementation outcomes, including adoption and fidelity of the intervention.
4D	Implementation Outcomes survey post-trial	To be completed by all participating GPs and practice staff of the intervention arm. Will be used to collect post-trial information from general practice staff. This survey will assess implementation outcomes, including adoption and fidelity of the intervention.
4E	General Practice Readiness for Change Questionnaire pre-trial	To be completed by a practice representative 'Practice Champion' from practices participating in the Pilot of a general practice-led intervention to increase National Bowel Cancer Screening Program participation . Will be used to assess practice 'readiness' to implement changes that support bowel cancer screening and to obtain practice staff demographics.
4F	General Practice Readiness for Change Questionnaire post-trial	To be completed by a practice representative 'Practice Champion' from practices participating in the Pilot of a

		general practice-led intervention to increase National Bowel Cancer Screening Program participation. Will be used to assess practice 'readiness' to implement changes that support bowel cancer screening and to obtain practice staff demographics.
4G	CTC Project Log	To document the steps taken to complete each implementation task, and the time and resources involved.
Ongoing trial monitoring activities		
5A	Delegation of duties	Pending
5B	Trial monitoring	Pending
6A	Intervention Design	Provides a description of the intervention components.

CTC=Clinical Trial Coordinator, GP=General practitioner, PHN=Primary Health Network, PCF=Participant information and Consent Form; PIS = Participant Information Sheet

6. Introduction

6.1. Background and rationale

Colorectal cancer (CRC) is the fourth most common cancer in Australia and screening for precancerous lesions and early stage cancer is proven to decrease CRC mortality and morbidity (1,2). In Australia, the National Bowel Cancer Screening Program (NBCSP) provides a self-administered stool test, the immunochemical faecal occult blood test (iFOBT), mailed to the home of all Australians aged 50-74 years. If an individual has above average risk of CRC (e.g., a family history of the disease), specialised screening regimens via colonoscopy are recommended in place of NBCSP screening (3). Optimising the NBCSP and ensuring people at above average risk are screening appropriately are critical to reducing CRC mortality and morbidity in Australia. The NBCSP alone has the potential to save 84,000 lives by 2040 if participation can reach and be sustained at 60% (4).

The CRC burden in Australia remains high and there are many people who do not screening according to the evidence-based guideline recommendations (3). That is, they either do not screen at all (under-screened) or screen using colonoscopy when they are not at above average risk (inappropriately screened). Under-screened individuals are at higher risk of developing advanced-stage CRC, whereas inappropriately screened individuals can place unnecessary strain on the healthcare system through low-value colonoscopies (5). Improving guideline-appropriate CRC screening will improve CRC outcomes and optimise the use of CRC-specific health services.

Evidence-based interventions can change screening behaviours and are generally targeted at the individual (e.g. personal reminders, modifications to simplify kit use, etc. (6)) or the whole of population (e.g. mass-media awareness campaigns (7)). Healthcare professionals, especially general practitioners (GPs), play a critical role in advocating for cancer screening (6,8) and have the clinical expertise to support guideline-appropriate care (9) but do not currently play an active role in the NBCSP. Existing Australian evidence suggests that GPs' perceptions of CRC screening can be improved by more formal engagement in the routine screening through the NBCSP (10). From 2020, the National Cancer Screening Register (NCSR) allowed GPs to access up to date patient specific screening history for the NBCSP. Additionally, a pilot program was launched by the Department of Health and Aged Care in late 2022 to enable GPs to provide NBCSP kits directly to an eligible patient during a regular consultation (11). More research is required to explore how to mobilise general practice to support guideline-appropriate CRC screening.

6.1.1. Current project and preliminary work conducted

The MAIL, GP & SCALE project (National Health and Medical Research Council: Targeted Call for Research 2021/GNT2014964) was designed to explore CRC screening behaviours in Australia and the involvement of GPs in the NBCSP. As part of the MAIL, GP and SCALE project, a preliminary evidence review has been conducted, which has identified effective evidence-based intervention components and implementation strategies for emerging and existing CRC screening interventions (12). The extracted data and other information were coded against the Expert Recommendations for Implementing Change (ERIC) and the Consolidated Framework for Implementation Research (CFIR) (13,14) to describe determinants affecting implementation and the effective strategies.

The information from the evidence review was then explored further as part of a co-design process with GPs and general practice staff completed in April 2023 (HREC 2022/755). The co-design included an analysis of participants' perspectives on CRC screening in general practice, the NBCSP, potential intervention components and implementation strategies, using ERIC and CFIR. Together, this has informed the design of a multicomponent intervention and implementation strategies for the MAIL, GP & SCALE trial.

6.2. Addressing the problem: a general practice led-intervention to increase NBCSP participation.

The MAIL, GP & SCALE trial is the pilot of a co-designed intervention to increase National Bowel Cancer Screening Program participation. The trial will use a two-arm cluster-randomised Hybrid Type 2 effectiveness-implementation randomised controlled trial (RCT) (15).

The MAIL, GP & SCALE co-designed intervention (also referred to as the intervention) will target general practice staff including GPs, practice nurses, practice managers and administrative staff and is multi-component. The intervention will include CRC decision support tools, point of care prompts, clinical system enhancement, and general practice staff education. The implementation of the intervention will be supported by Clinical Trial Co-ordinators (CTCs) with a suite of co-designed strategies to facilitate behaviour change and the recommendation of guideline-appropriate CRC screening.

7. Aim, objectives, and hypothesis

8.1. Primary Outcomes

The trial will evaluate the primary outcomes of implementation and clinical effectiveness of the intervention by general practice.

- A. The co-primary **implementation effectiveness outcome** is guideline-appropriate CRC screening recommendations provided.
- B. The co-primary **clinical effectiveness outcome** is guideline-appropriate CRC screening tests completed by patients.

8.2. Secondary Outcomes

The secondary trial outcomes include service and implementation outcomes by general practice.

- A. The **service outcome** is general practice awareness and understanding of guideline-appropriate screening.

- B. The **implementation outcome** is the adoption of in-practice activities and implementation strategies to support CRC screening.

The outcomes will be reported in accordance with the Consolidated Standards of Reporting Trials (16). Previous work on the theory-grounded implementation method for translating clinical guidelines and policy into practice – the Theoretical Domains Framework Implementation approach (TDFI) (17–19) – will be adapted. This is a proven method to help healthcare professionals deliver evidence-based care. As this trial will support guideline-appropriate CRC screening in general practices, the TDFI will be critical to implementing the trial intervention. The type and quality of the implementation strategies will be described and reported according to the StaRI Statement and Checklist (20).

9. Participating Sites

The trial will be conducted in up to 100 general practices in NSW and WA in one of the following Primary Health Networks (PHNs):

- Central and Eastern Sydney
- Perth North
- Perth South

PHNs provide ongoing support to general practices in Australia to deliver high-quality care (21). PHN regions have been selected based on Australian Institute of Health and Welfare (AIHW) NBCSP screening participation and cancer diagnoses data (22).

The Department of Health PHN Grant Programme Guidelines outlines the PHN's role to support continuous improvement, including research (21). PHNs hold formal Data Sharing Agreements with general practices in their regions, including a framework for PHN collection, aggregation, and analysis of general practice data via data extraction tools. PHN Data Sharing Agreements permit third parties to use de-identified and aggregate data collected for research purposes.

The Daffodil Centre, a joint venture between Cancer Council NSW and the University of Sydney, is the coordinating centre of the study. Each participating PHN will enter into a Standard Clinical Trial Agreement with the University of Sydney that outlines the trial schedule and the PHN role at a participating site. The Agreement will outline the objectives of the study and support of the PHN in recruitment of practices and facilitation of general practice data collection and sharing ([see section 10.4](#)). The executed Agreement will permit the use of de-identified aggregate general practice data to be shared with The Daffodil Centre for the research purposes of the trial. The Agreement will outline the management and use of the data in accordance with published guidance material and the Australian Code for the Responsible Conduct of Research, 2018 (23). Individual data-sharing agreements will not be needed between the Daffodil Centre and participating general practices.

9.1. Clinical trial coordinators (CTCs)

Four CTCs, two per state, will be appointed to coordinate trial activities and to undertake data collection. MAIL, GP & SCALE funding will support four x 0.8 FTE positions for one year. Ideally, the CTCs will have a professional understanding of primary care, cancer screening, the ability to learn implementation techniques, and the ability to engage with and motivate participating general practices.

Each CTC will be employed either by the PHN or through the University of Sydney as contract employees and trained by The Daffodil Centre research team. The CTCs will be trained to understand

their responsibilities to conduct ethical research and be provided with a Project Log for record keeping (Appendix 4G). In addition, CTCs will receive support and training in strategies to improve the implementation of the intervention in the primary healthcare setting. A previously developed training toolkit and 1-day course will be refined for the MAIL, GP & SCALE trial (18). Each CTC will be responsible for 25 general practices that will be a combination of intervention and control sites.

10. Research Plan

10.1. Study design

10.1.1. Cluster-randomised hybrid type 2 effectiveness-implementation trial

The MAIL, GP & SCALE trial is a hybrid type 2 effectiveness-implementation trial that will be conducted in up to 100 general practices. It will test the clinical and implementation effectiveness of the intervention and a suite of implementation strategies. The trial has been designed as a pilot as the outcomes are essential to inform a later objective of the broader MAIL, GP & SCALE project for intervention sustainably and scaled-up in general practices across Australia.

10.1.2. Population & sample size

An indicative sample size has been calculated based on documented approximate rules for pilot trials (24). For a main trial designed with 90% power and two-sided 5% significance, pilot trial sample sizes with 50-75 practices per arm for standardised effect sizes ranging from extra small (≤ 0.1) to large (0.8) are recommended (24). We aim to recruit up to 50 general practices per arm with at least two GPs per practice, in line with previous studies despite the sample size calculated based on patient screening behaviour change (25,26). A pilot with up to 100 general practices will yield sufficient information to assess the effectiveness of the intervention.

10.1.3. Recruitment of participating general practices

The PHNs will provide a list of potentially eligible general practices to the CTC. The CTCs will be responsible for facilitating recruitment with support from the PHN. PHNs communicate directly to general practice via practice-approved email updates, website updates and newsletters. Eligible general practices will be sent an email inviting them to participate by the CTC (Appendix 1A). The email will contain information about the trial and a link directing them to a research landing page on Redcap where they may submit an expression of interest form. CTCs may call practices that have not yet expressed interest and provide information about the trial over the phone. If the practice is not interested, no further contact will be made. In addition, PHNs may circulate information about the study through their communication channels such as emails and newsletters. Information circulated will contain a link to the online REDCap landing page where practices may read the Participant Information Statement and provide digital consent.

The CTCs will follow up practices that have expressed interest. CTCs will email additional trial information and will continue to follow-up with interested practices up to three times by phone and/or email. After three failed follow-up attempts, it will be assumed that the practice is no longer interested in taking part in the trial. As part of the recruitment process, CTCs will establish practice eligibility based on the following criteria.

- Inclusion criteria:
 - Has at least two GPs (2 FTE) willing to participate in the trial
 - Nominated Practice Champion who is willing and able to liaise with the CTC
 - Uses Medical Director software
 - Uses Pen CS, Polar or Primary Sense

- Available over the trial period October 2023 – October 2024
- Windows 10 or higher, i5/i7 16GB processing or willing to upgrade
- Has over 1000 active patients and sees minimum of 35 adult patients per day
- Exclusion criteria:
 - Shares server with another practice
 - Uses paper-based medical records
 - Does not share data with PHN

Exclusion criteria is based on the need to deliver the intervention using the Clinical Information Systems (CIS) (or practice software) in the general practice.

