10.5. Allocation and blinding process

Randomisation for this study will be carried out at the level of general practice. Each practice will be allocated to the intervention or usual care arm using a random computer-generated sequence by the Daffodil Centre research team. To account for differences in region-specific NBCSP screening rates, the randomisation will be stratified by participating states (NSW and WA). In each state, the same number of practices will be allocated to the intervention and usual care arms. Accordingly, GPs, general practice staff and their patients will be assigned to the intervention or usual care arm based on the assignment of their general practice.

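### Eligibility and allocation have no rule for a GP or staff member who works at two enrolled practices, so one person can fall in both arms; the likely dilution is small and the remedy cheap

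*Protocol*

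**What the plan says.** The Synopsis and Section 10.1.3 of the protocol list the same three exclusions: a practice that "Shares server with another practice", one that keeps paper records, and one that "Does not share data with PHN". Section 10.1.3 explains the exclusions by the need to deliver the intervention through the practice software. Contamination between arms is not mentioned.

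The GP criterion is worded in full-time equivalents. Section 10.1.3 has "Has at least two GPs (2 FTE) willing to participate in the trial" and the Synopsis has "Has at least two full-time equivalent GPs willing to participate in the trial". Neither requires that a participating GP work at only one enrolled practice.

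Section 10.5 states: "Randomisation for this study will be carried out at the level of general practice". It stratifies by state and adds that "GPs, general practice staff and their patients will be assigned to the intervention or usual care arm based on the assignment of their general practice".

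On earlier exposure, Section 6.1.1 describes a "co-design process with GPs and general practice staff completed in April 2023", and Section 10.2.1 says its participants assessed the intervention components. The wash-out in Section 10.2 and the remark on prior exposure in Section 10.2.1 concern general screening-programme material, not shared staff.

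**The concern.** Assigning people through their practice works only if each person belongs to one enrolled practice, and nothing in the eligibility or allocation text secures that. All practices come from three Primary Health Networks (Section 9), and an FTE criterion can be met by part-time GPs, so overlap is possible. A GP trained in an intervention practice could take the education, decision aids and communication checklist (Section 10.2.1, Table 1) into a control practice. That would pull both co-primary comparisons toward no difference and blur the awareness outcome.

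Although labelled a pilot, the trial tests two hypotheses for statistical significance (Section 7), and its results feed a national predictive model and a scale-up recommendation (Section 15). Avoidable dilution would carry forward into both.

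**Working it through.** **Does anything later in the protocol catch the problem?**

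- Section 10.1.4 (withdrawal): a GP who withdraws is replaced if possible. There is no check on where the replacement also works.
- Section 10.4: the estimating equations cluster by practice, so practices are treated as independent. Shared GPs break this.
- Section 11.1.2: each coordinator assigns participant numbers for their own sites and cannot see files from other sites. A GP consenting under two coordinators could receive two numbers unnoticed.

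None of these closes the gap.

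**Size.** There is no stated figure to reproduce. The sample size in Section 10.1.2 rests on a cited rule for pilot trials, and no target effect or intra-practice correlation is given. The following shows scale only.

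Inputs from the protocol:
- 25 practices per arm in each state (Synopsis), hence 50 control practices.
- Minimum 2 FTE of participating GPs per practice (Section 10.1.3).

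Assumptions:
- 4 to 10 linked pairs, each within one state. The documents give no count.
- The shared GP works 0.5 FTE at the control practice.
- That GP's exposure carries over completely, and influence is proportional to FTE.

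Steps:
1. Probability that a linked pair is split: fix one practice. Of the other 49 in the state, 25 are in the opposite arm, so 25/49 = 0.510.
2. Expected split pairs: 4 × 0.510 = 2.04; 10 × 0.510 = 5.10.
3. Exposed share of each affected control practice: 0.5/2 = 25%.
4. Dilution c over 50 control practices: 2.04 × 0.25/50 = 1.0%; 5.10 × 0.25/50 = 2.55%.
5. Effective sample size, (1 − c)²: 0.9898² = 0.98; 0.9745² = 0.95.
6. Power: with 50 practices per arm, the practice-level standardised difference detectable with 90% power (two-sided 5%) is (1.960 + 1.282) × √(2/50) = 0.648. Diluted power is Φ(3.242 × (1 − c) − 1.960). This gives Φ(1.249) = 89.4% for 4 pairs and Φ(1.199) = 88.5% for 10.

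Section 7 gives 50 practices per arm in each state, which conflicts with the Synopsis and with the total of up to 100. On that reading step 1 becomes 50/99 = 0.505. With 100 control practices, the dilution in step 4 roughly halves.

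**The case against.** The strongest reply is that this is an omission with little effect. The server exclusion does what it was written to do. The prompt and the system changes sit in the practice software, and audit, feedback and coordinator support are delivered to the intervention practice (Sections 10.2.1 and 10.2.2), so mainly education and decision-aid use can travel with a GP. The clinical co-primary uses aggregate extracts from practices with over 1000 active patients, and not all staff need take part, so one GP's weight may be smaller still. The recruitment templates (Appendices 1A and 1B) are not shown and may already ask about other workplaces.

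The argument on size stands. The gap remains: even if a form asks the question, Section 10.5 has no rule for acting on the answer, and an analysis plan cannot use links that were never recorded.

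Two stronger readings are tempting. A reader might count one shared GP as half of a two-GP practice, giving 2 to 5% dilution and an effective sample size of 96 to 90%. The 2 FTE rule does not support this. If only two GPs make up 2 FTE, both are full-time and have little room for a second post; if part-timers make it up, there are more than two.

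A reader might also infer that co-design practices must be excluded. The documents do not say how many co-designers there were or where they practised. They assessed components drawn from existing tools and did not receive supported delivery. The acceptability survey they might rate favourably is given in the intervention arm only (Section 10.3.2), so it cannot bias a comparison between arms.

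**Conclusion.** The concern holds as a gap in eligibility and allocation: the protocol as written can place one GP in both arms. Its likely size is small. Dilution is about 1 to 2.5% and effective sample size about 98 to 95%, if there are 4 to 10 linked pairs within a state and the shared GP is half-time. Both inputs are assumptions. Complete carry-over is also assumed, so for those inputs the figures are upper limits.

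It would go too far to say that the harm cannot be undone after randomisation. If links and co-design participation are recorded beforehand, the primary analyses can be repeated without the affected practices. If they are not recorded, that option is lost. Low to moderate priority.

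**What to change.** - On the expression-of-interest or consent form, before allocation, ask which other practices each participating GP, nurse and Practice Champion works in.
- In Section 10.5, state that enrolled practices sharing participating staff are randomised as one unit to the same arm, or that only one of them is enrolled. If they are joined, the analysis should treat them as one cluster.
- In Section 10.1.4, apply the same check to any replacement GP.
- Record before allocation whether a practice's staff took part in the co-design (HREC 2022/755), for a sensitivity analysis without those practices. It need not be an exclusion.

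The cost is one question on an existing form, one sentence in each of two sections, and slightly fewer independent clusters where practices are joined or one is left out.
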